Oxidative Stress and COPD. A shift in the antioxidant/free radical balance in favour of free radicals is termed oxidative stress. Superoxide anion (O_2^-) and other free radicals are highly energized molecular species, structurally distinct in that they contain one or more unpaired electrons in their atomic orbital ³³. Although low concentrations of free radicals appear to have important roles in cell signaling, an excess of free radicals can cause a wide spectrum of cellular damage, including lipid peroxidation, alteration of

intracellular redox state, inactivation of enzymes, and damage to DNA. Unsurprisingly, elevated oxidative stress has been observed in smokers³⁴⁻³⁶ and in COPD^{24, 37}. Since the initial observation that O_2^- and other free radicals inactivate nitric oxide³⁸, which plays a fundamental role in regulating endothelial function, it seems logical that the elevated oxidative stress observed in COPD would contribute to endothelial dysfunction. One method to reduce oxidative stress is through a reduction in superoxide anion (O_2^-), which would limit the degradation of NO, thus increasing its bioavailability. Antioxidant supplementation has been utilized as a means to reduce oxygen free radicals and increase NO bioavailability in several clinical populations³⁹⁻⁴¹.

3. Inclusion and Exclusion Criteria

List the inclusion/exclusion criteria:

- Inclusion
 - o 24 patients with medically diagnosed COPD
 - 24 apparently healthy controls
- Exclusion
 - FEV1/FVC >0.7 (normal lung function in patients only)
 - Clinical diagnosis of heart disease or diabetes
 - Vasoactive medications (i.e. nitrates, beta-blockers, Viagra etc.)
 - o uncontrolled high blood pressure
 - high blood pressure in your lungs
 - o thyroid problems
 - o Fluid in the lungs
 - Sleep apnea
 - o Anemia
 - o Raynaud's Phenomenon
 - o GI bleeding
 - Gangrene of the digits
 - History of low platelets or coagulopathies
 - Phenylketonuria (PKU)
 - o Pregnant
 - Lactation
 - Any allergy to Kuvan

4. Number of Subjects/Records/Samples Collected

A maximum of 48 volunteers will be needed for this entire research study. For patients, there are 2 protocols which each consist of 6 visits each. We would like to recruit 12 patients with COPD that will be asked to complete the Kuvan protocol and an additional 12 patients that will be asked to complete the Antioxidant protocol. Apparently healthy controls (n=24) will be asked to only complete visit one.

5. Recruitment Methods

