In this study there will be 5 experimental visits following the preliminary visit each being four weeks apart. For the Kuvan (BH4) protocol, depending on the randomized group the subject is in they will receive either 5 mg, 10 mg, or 20 mg per kg of treatment.

Tentative Schedule of Events:

*Note subject may or may not be asked to perform all procedures during each testing day depending on

time and availability. Also, some preliminary day measures may not be completed on the preliminary day and may be completed some other time during the course of the study.*

Preliminary Day

- Consent
- ABI
- IMT
- DXA Scan
- Pulmonary Function Test
- 6 min Walk Test

Experimental Testing Days

- Continued consent
- PWV
- FMD
- Skin Blood Flow/Local Heating
- Blood Draw
- Pulmonary Function Test

Risk Assessment

All procedures in this study have been routinely performed in research studies in the past and are of low risk to participants.

Venous Blood Draw. Potential risks related with taking a blood sample are few but include slight bruising, pain, a temporary feeling of faintness, and phlebitis. Rarely, there may be a small blood clot or infection at the site of the needle puncture. All blood draws will be performed by a research team member or a nurse who is certified in drawing blood; in either case sterile techniques will be used.

Pulmonary Function Test. There are no known risks associated with this test.

Muscle Function Test. Electrical stimulation of the muscles may be uncomfortable and could be painful. If the muscle stimulation is too painful, we will adjust the stimulation to a level that the subject can tolerate. The study does not require the stimulation to be painful for the study to be successful. Because the stimulator "exercises" the muscle, the muscle may be sore for a few days following the protocol.

Body Composition. The DXA will expose the subject to a minimal amount of radiation. The DXA scan will expose the participants body to about 3 mrem per scan. Everyone receives a small amount of unavoidable background radiation from the natural environment each year. The radiation dose from the DXA scan is equal to less than three to four extra days' worth of natural background radiation. Radiation at significantly higher levels is known to cause cancer; however, the amount of radiation in this study is very low and is not expected to cause bodily injury during the subject's lifetime. The radiation dose discussed

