Six-Minute Walk Test: Potential risk related to this test are few but include chest pain, shortness of breath, leg cramps, staggering, sweating, and pale skin color in the face. Every effort will be made to minimize these risks. A staff member who is certified in basic life support will be present at all times. We will have a chair available throughout the test if the patient needs to take a break. Oxygen will also be readily available.

Local Heating: We measure the temperature of the subject's skin under the ring holders. The skin will feel very warm but should not hurt. The heating of the water will make the skin of the subjects arm under the holders red like when taking a hot bath. The redness will not last more than a few hours. Some people may be more sensitive to the heating than others. If the subjects arm feels too hot, the subject has been instructed to tell us, and we will reduce or stop the heating.

Visits Required:

There are six visits required for all COPD subjects for this study, a preliminary visit, and 5 experimental day visits (baseline, 4 weeks, 8 weeks, 12 weeks, and a follow up visit on week 16). Control subjects will need to only complete one experimental day visit.

Subjects may participate in both protocols but they do not have to. If they do wish to participate in both protocols, they must wait at least 4 weeks in between protocols.

Click here to enter text.

7. Data and Specimen Management

a. Describe the data analysis plan, including any statistical procedures: The proposed investigation is an open-label dose response investigation. More importantly, this investigation is a pilot project that is based on the transient findings of previous funded American Heart Association grant. Nonetheless, for the Kuvan protoco we will employ a 3 x 5 (dose x time) mixed factorial ANOVA with the repeated factor being time. For the Antioxidant protocol we will employ a Repeated measures ANOVA For both protocols we will run planned comparisons of the treatment response to the control data to determine the effects of the treatment relative to the baseline value of the control. In an attempt to reduce the family wise error rate, planned comparisons will als be made for the interaction between baseline and 12 weeks for each dose with comparison made with the withdraw period.	our l A. Soo ons	
b. When applicable, provide a power analysis:	□ N/A	
The power and sample sizes could not be determined from the acute intervention study.		

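### The Kuvan 3 x 5 ANOVA enters baseline and week 16 as outcome levels and names no baseline covariate, so the dose main effect is diluted and the baseline-to-week-12 change is less precise than it could be

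*Combined protocol and SAP*

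**What the plan says.** Section 7a specifies the Kuvan analysis in one sentence: "we will employ a 3 x 5 (dose x time) mixed factorial ANOVA with the repeated factor being time". Section 6, Visits Required, lists the "5 experimental day visits (baseline, 4 weeks, 8 weeks, 12 weeks, and a follow up visit on week 16"; these five visits are the five time levels. Section 7a then adds that "planned comparisons will als be made for the interaction between baseline and 12 weeks for each dose with comparison made with the withdraw period". It names no covariate and does not say which term of the ANOVA answers the dose question.

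On design, section 6 states that "depending on the randomized group the subject is in they will receive either 5 mg, 10 mg, or 20 mg per kg of treatment", and section 4 says "We would like to recruit 12 patients with COPD that will be asked to complete the Kuvan protocol". The allocation ratio is not given; equal allocation would put 4 patients on each dose. Section 7b states: "The power and sample sizes could not be determined from the acute intervention study". No effect size, SD, alpha or within-patient correlation appears anywhere.

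**The concern.** Dose is the only randomised comparison in the study, and about 4 patients per dose carry it. Two features of the model work against it.

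First, the dose main effect is standard output of a mixed ANOVA. Here it averages the dose difference over a visit where treatment cannot yet have acted and over a visit that is probably off treatment. The study calls itself a dose-response investigation, so a null main effect could easily be reported as no dose response.

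Second, each patient's baseline value is collected but enters only as another outcome level. The within-patient contrasts then subtract baseline in full. With few patients and moderate correlation between visits, full subtraction adds noise that a covariate would avoid.

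**Working it through.** The plan states no power or effect figure, so there is nothing of its own to reproduce. The structural inputs (3 doses, 5 visits, 12 patients) come from sections 4, 6 and 7a. All other inputs below are assumptions.

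**Step 1: dilution of the dose main effect.** The main effect is the unweighted mean of the dose difference over five visits. Let D be the difference at week 12.

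| Time course | Five-visit mean | Share of D |
|---|---|---|
| Constant at weeks 4-12, nothing at week 16 | (0+1+1+1+0)/5 | 0.6 |
| Constant, half carried over | (0+1+1+1+0.5)/5 | 0.7 |
| Constant, full carry-over | (0+1+1+1+1)/5 | 0.8 |
| Linear build-up, nothing at week 16 | (0+1/3+2/3+1+0)/5 | 0.4 |
| Week 12 only | (0+0+0+1+0)/5 | 0.2 |

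The loss relative to week 12 therefore runs from 20% to 80%. Relative to the on-treatment mean it is 40% whenever week 16 carries no dose effect; for linear build-up, 0.4/(2/3) = 0.6. The interaction and the baseline-to-week-12 contrast are differences across time, so this dilution does not reach them.

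**Step 2: change score against covariate at week 12.** Take visit SD 1 and correlation r between baseline and week 12. The change has variance 2(1 - r). The baseline-adjusted value has residual variance 1 - r². Their ratio, adjusted to change, is (1 + r)/2:
- r = 0.3: 0.65
- r = 0.5: 0.75
- r = 0.7: 0.85
- AR(1) 0.7, three visits apart: r = 0.7³ = 0.343, ratio 0.67

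Error degrees of freedom are 12 - 3 = 9 for the change and 12 - 3 - 1 = 8 with the covariate.

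**Step 3: simulated power.** Assumptions: 4 patients per dose, SD 1, top dose 1.5 SD above bottom with the middle dose halfway, alpha 0.05, constant effect at weeks 4 to 12 and none at week 16. Tests: main effect F(2,9), interaction F(8,36), change F(2,9), baseline-adjusted F(2,8). There were 20,000 to 40,000 trials per case. Repeated runs differ by about one point, and ranges quoted in the text take the widest values.

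| Visit correlation | Dose main effect | Dose x time interaction | Week 12 change | Week 12 adjusted | Mean of weeks 4-12 adjusted |
|---|---|---|---|---|---|
| 0.3 equal | 29% | 38% | 26% | 33% | 60% |
| 0.5 equal | 22% | 52% | 34% | 39% | 63% |
| 0.7 equal | 18% | 79% | 53% | 54% | 76% |
| AR(1) 0.7 | 21% | 37%* | 27% | 34% | 55% |

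*With Greenhouse-Geisser correction; uncorrected, the interaction rejects nearly 8% under the null in this case. The other interaction figures are uncorrected.

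For the mean of weeks 4 to 12, the change score has 36-72% against 55-76% adjusted.

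**Step 4: other time courses** (correlations 0.5 / 0.7 / AR(1) 0.7).
- Constant effect, full carry-over: main effect 36 / 30 / 36%, against 63 / 76 / 56% for the adjusted mean.
- Linear build-up, full washout: main effect 12 / 10 / 12%, adjusted mean 33 / 41 / 28%, adjusted week 12 39 / 54 / 34%.

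**The case against.** The strongest reply is that section 7a already has a baseline-referenced dose comparison. The baseline-to-week-12 contrast by dose subtracts each patient's own baseline, and the interaction removes any stable difference between groups. The plan never names the dose main effect as its deciding test, so the main-effect power is not the power of the planned inference. All of that stands. A reader might infer that baseline goes unused, or that the planned dose test is itself diluted; the text supports neither.

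A reader might also take 40% as the loss. That figure needs no remaining dose effect at week 16 and is measured against the on-treatment mean. No section gives the last dosing day, and that week 16 is off treatment is inferred from the references to withdrawal and follow-up.

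Nor is baseline adjustment always the most powerful choice. The 8-df interaction is about level with it at high correlation (79% against 76% at 0.7; about 100% against 99% at 0.9), although it gives no dose estimate or direction. At 0.9 the covariate no longer gains on the change score either: for the mean of weeks 4 to 12, 98.8% against 99.4%.

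Finally, if washout is complete, week 16 is a second off-treatment reference. Week 12 minus the mean of baseline and week 16 reaches 44 / 66 / 55% (correlations 0.5 / 0.7 / AR(1) 0.7), against 39 / 54 / 34% for baseline-adjusted week 12. With half or full carry-over that advantage is lost. Leaving week 16 out therefore cannot be claimed as a gain in power.

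**Conclusion.** The point holds in limited form. Baseline and week 16 are two of the five outcome levels, and baseline is not a covariate. The main effect shows 0.6 to 0.8 of a constant on-treatment dose difference, depending on carry-over, and less than 0.6 of the week 12 difference if the effect builds up over time without carry-over. The change contrast is undiluted but less efficient than a covariate at correlations of 0.3 to 0.7. The gain from adjustment at week 12 is about 1 to 7 points of power. The adjusted mean of weeks 4 to 12 beats the five-visit main effect in every case shown.

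The power figures rest on assumed effect size, correlation, time course and equal allocation, none of which the documents give. They show the ordering of methods, not the power of this trial. For an open-label pilot this is a gap in specification with a cheap remedy; the planned contrasts remain valid.

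**What to change.** In section 7a:
- Estimate the dose differences at week 12 and for the mean of weeks 4 to 12, each with the patient's own baseline value as a covariate.
- State in advance which of the two is the main estimate. Week 12 does better if the effect builds up, the mean if it is constant.
- State that the dose conclusion will not rest on the five-visit dose main effect.
- Keep the planned withdrawal comparison with week 16 as a separate contrast, with no claim that leaving week 16 out of the dose model gains power.

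The cost is wording in 7a and one error degree of freedom (8 instead of 9). It needs no extra patients, visits or measurements.

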13. Consent Process

On the preliminary visit when subjects first arrive they will be undergo the informed consent process. The RA will go over everything that will be involved in the study in detail. If the subject understands they will be asked to initial each page after the RA has explained that page of the document to them. The RA will answer any questions the subject may have during the consent process. In addition, when finished going through the ICD, the RA will ask the subject again if he/she has any questions and will get confirmation that the subject still wants to participate in the study. If the subject agrees they will sign the document on the last page followed by the RA's signature indicating the subject understands everything. [name] will confirm that the subjects understand the study and are still willing to participate. [name] will also answer any questions that the subjects might have. All subjects will be aware that they have the right to stop the test at any time.

14. Compensation for Research-Related Injury

This section is not required when research involves no more than Minimal Risk to subjects. \Box N/A

Because of Georgia Regents University policy, the institution is not able to offer financial compensation should the subject be injured as a result of participating in this research. However, the subject is not precluded from seeking to collect compensation for injury related to malpractice, fault, or blame on the part of those involved in the research, including the institution. Each risk described has been considered and all safety precautions have been put in place to protect the subject. The subjects are aware if they have any questions or concerns during the study they will need contact us immediately.

15. Resources Available

\square N/A

The study doctor, [name], will be on hand to work with patients if a medical consequence occurs as a result of the research. Patients will also be directed to the GRU clinics or ER if necessary. If the issue is psychosocial, then patients will be directed to the GRU Psychology department to talk to one of the licensed and trained psychologists on staff.

All research staff are required to sign by their duties associated with each study that they understand and know how to carry out their duties in any event. These documents can be found in the HAC binders in the office of the PI.

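### Section 7a compares treated patients with healthy controls seen once in order to determine treatment effects, but those controls can only supply a reference level

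*Combined protocol and SAP*

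**What the plan says.** The analysis plan is in section 7a of the combined protocol and SAP. It describes an open-label pilot and names these analyses:

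- Kuvan protocol: a 3 x 5 dose-by-time mixed ANOVA. Section 6 says the dose groups are randomised.
- Antioxidant protocol: "For the Antioxidant protocol we will employ a Repeated measures ANOVA".
- Both protocols: planned "comparisons of the treatment response to the control data to determine the effects of the treatment relative to the baseline value of the control".
- A further planned comparison for the "interaction between baseline and 12 weeks for each dose with comparison made with the withdraw period".

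Treatment response is not defined. Section 3 gives the control group as 24 apparently healthy people. Sections 4 and 6 both have them seen once, in different words: "Apparently healthy controls (n=24) will be asked to only complete visit one" (section 4) and "Control subjects will need to only complete one experimental day visit" (section 6, Visits Required). No untreated or placebo COPD group is described. In section 2, the paragraph on vascular endothelial function reports that FMD has been found impaired in COPD, so the groups are expected to differ before any treatment.

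Section 4 asks for 12 patients in each protocol and does not state how the Kuvan patients divide among the three doses. Section 7b gives no power calculation.

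**The concern.** The stated purpose of the control comparison is to determine treatment effects. A comparison can do that only if its expected value is zero when the treatment does nothing, or if the controls show what would have happened to patients without treatment. Healthy people measured once meet neither condition.

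If a report follows the wording of 7a, a difference that reflects disease could be presented as a treatment effect. Equally, a non-significant difference in a small sample could be presented as restored vascular function. Section 7a gives no rule for interpreting either result.

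**Working it through.** The plan gives no effect size, SD, alpha or power, so there is no figure to reproduce. The main result is algebra; the percentages only illustrate it.

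**Inputs from the documents.** 12 patients per protocol, three Kuvan doses, 24 controls (sections 3, 4 and 6); patient visits at baseline and weeks 4, 8, 12 and 16 (section 6).

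**Assumptions.** Two-sided alpha 0.05, equal SDs (set to 1), complete data, no drift over visits, a baseline COPD-control gap of 0.5 to 1.5 SD, and 4 patients per Kuvan dose if the split is equal.

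**Step 1: each reading of the comparison.** Let P0 and P12 be the patient means at baseline and week 12, and C the single control mean.

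- *On-treatment level v control.* P12 - C = (P0 - C) + (P12 - P0), which is the disease gap plus the patient change. An inert treatment leaves the gap, so the expected difference is not zero.
- *Change v control.* P12 - P0 is a change. Controls have one value, so they have no change to set beside it.
- *Gap after minus gap before.* (P12 - C) - (P0 - C) = P12 - P0. The control mean cancels.
- *Share of the gap closed.* (P12 - P0)/(C - P0). The control mean only rescales; no change is still tested by the numerator, which uses patients alone.

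**Step 2: do the controls add precision?** With within-patient correlation r (assumed), the standard error of the change is sqrt(2(1 - r)/12), or 0.342, 0.289 and 0.183 SD at r = 0.3, 0.5 and 0.8. A generalised least squares fit with the 24 controls added gives the same three values.

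**Step 3: how often is an inert treatment significantly different from controls at week 12?** This is the power of a two-sample t-test at the size of the gap, from the noncentral t with noncentrality d / sqrt(1/n + 1/24) and n + 22 degrees of freedom.

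| Gap d (SD) | 12 v 24 (antioxidant, or Kuvan doses pooled) | 4 v 24 (one Kuvan dose, equal split) |
|---|---|---|
| 0.5 | 28% | 14% |
| 1.0 | 78% | 43% |
| 1.5 | 98% | 76% |

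**Step 4: the opposite error.** Suppose treatment closes half of a 1 SD gap, leaving 0.5 SD. With 12 v 24 the test is significant in 28% of trials, so it is non-significant in 100 - 28 = 72% although half the gap remains. If treatment closes the whole 1 SD gap, the control comparison is significant in only 5%, while a paired baseline-to-week-12 test in the 12 patients (r = 0.5) is significant in 88%. The control test is thus least likely to be significant when the treatment works completely.

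**Step 5: precision as a benchmark.** The 95% CI half-width is t x sqrt(1/n + 1/24).

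- 12 v 24: 2.032 x 0.354 = 0.72 SD.
- 4 v 24: 2.056 x 0.540 = 1.11 SD.

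**Step 6: which visit do controls attend?** Section 6 states "In this study there will be 5 experimental visits following the preliminary visit each being four weeks apart", and section 13 states "On the preliminary visit when subjects first arrive they will be undergo the informed consent process". For patients, then, the first visit is the preliminary day, whose procedure list has neither FMD nor PWV; the experimental-day list has both. Section 4 read literally points to the first list and Visits Required to the second.

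**The case against.** The strongest reply is that the sentence ends by referring to the control's baseline value, which naturally describes a healthy reference level, and that nothing in the documents says a difference from controls will be claimed as efficacy. This stands in part. The benchmark reading is available and legitimate, and the harm depends on how the result is reported. But the purpose given is still to determine treatment effects, and 7a does not restrict the comparison to a benchmark.

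A second reply is that treatment inference has its own analyses. That is correct. A reader might infer that 7a has no usable treatment analysis, but the documents do not support this: the dose-by-time contrast is between randomised groups, and the baseline, week-12 and withdrawal comparison is within patients. The withdrawal visit also gives a partial check on steady drift. The defect is confined to the control comparison.

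A reader might also infer that controls will have no FMD or PWV data. That goes too far. Visits Required gives controls an experimental day, whose list includes both measures, so this is a conflict of wording. The schedule note that a "subject may or may not be asked to perform all procedures during each testing day depending on" time and availability applies to every subject, not to controls in particular.

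Finally, a reader might infer that the antioxidant protocol has no within-patient planned comparison, since that comparison is written per dose. The text is unclear rather than silent: the cocktail has a single composition, and the preceding sentence covers both protocols. Naming the protocol would settle it.

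**Conclusion.** The concern holds as a fault in the stated purpose of one planned comparison, and it should be fixed. That single-visit healthy controls give a reference level and no information on the treatment effect follows from the design and needs no numerical assumption.

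The size of the possible misreading does rest on assumptions: the gap is not given in the documents, and equal SDs, complete data, no drift and two-sided 0.05 are assumed. The 12 v 24 figures apply to the antioxidant protocol or to pooled Kuvan doses. The 4 v 24 figures apply to a single Kuvan dose only if patients are split equally, which is not stated.

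The other 7a analyses are unaffected, and the conflict over the control visit is a secondary point of wording.

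**What to change.** 1. In 7a, delete the purpose of determining treatment effects from the control comparison. Define it as a descriptive benchmark: COPD minus control at baseline and at week 12, each with a 95% CI. State the expected half-widths (about 0.72 SD for 12 v 24, about 1.11 SD for 4 v 24 if the Kuvan split is equal) and say that a non-significant difference will not be read as normalisation.
2. State that treatment inference rests on analyses already in 7a: the randomised dose-by-time contrast for Kuvan, and the within-patient baseline, week-12 and withdrawal (week-16) comparison in both protocols, with the antioxidant protocol named. Add that, without an untreated COPD group, the within-patient change is open-label and uncontrolled.
3. Reconcile the control visit in section 4 with that in section 6, so that it is clear controls have FMD and PWV measured.

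The cost is wording in sections 4, 6 and 7a, with no added visits if controls attend an experimental day as section 6 says. If only the preliminary day was meant, FMD and PWV would have to be added to it or the benchmark dropped for those measures. The downside is that the control comparison can no longer be presented as a treatment effect.
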